6.6.2.1.3 PF-IQOLS

Missing item scores are imputed by using the average of all available individual dimension ratings (items 1-16) for the missing item. If the missing items are >50%, then the PF-IQOLS score is set to missing.

6.6.2.2 Time-to-event endpoints

In the analyses of the time-to-event endpoints, missing or incomplete data will be managed by standard survival analysis techniques (i.e. censoring).

For the time to first acute ILD exacerbation, or first non-elective hospitalization in case of partially missing dates, the following imputation will be done:

- If day is missing, then imputed day will be the 15th of the month
- If day and month are missing, then imputed date will be the 1st of July of the (non-missing) year
- If year is missing, date will not be imputed

A missing or incomplete date of death will be imputed/completed so that the derived date is the earliest possible date which is on or after date of onset of the fatal AE, and on or after treatment start (in case this AE is treatment emergent), and on or after date of last contact.

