5.2.2.1.3 Time to first acute ILD exacerbation or death over 52 weeks

Acute ILD exacerbation is defined in the CTP as an acute, clinically significant, respiratory deterioration characterized by evidence of new widespread alveolar abnormality with all of the following:

- Previous or concurrent diagnosis of ILD
- Acute worsening or development of dyspnoea typically less than one month duration
- Computed tomography with new bilateral ground-glass opacity and/or consolidation superimposed on a background pattern consistent with fibrosing ILD
- Deterioration not fully explained by cardiac failure or fluid overload

Events that are clinically considered to meet the definition of acute exacerbation but fail to meet all four diagnostic criteria due to missing CT data should be termed “suspected acute exacerbations”. Please note that only acute ILD exacerbations that fulfil all the criteria depicted above will be taken into account and contribute to the endpoint. Information on acute ILD exacerbations will be obtained from the Adverse Events page.

For those patients who either experience acute ILD exacerbations or who die due to any cause within the first 52 weeks, time to first acute ILD exacerbation or death [days] will be computed as:

- Earliest of date of first documented acute ILD exacerbation or death – date of first drug intake + 1

Patients who did not experience any ILD exacerbation event within the first 52 weeks will be censored according to the mechanism for censoring as described in [Table 5.2.2.1.3: 1](#).

Table 5.2.2.1.3: 1 Censoring Rules for Time to first acute ILD exacerbation or death over 52 weeks

Rule #	Situation	Outcome (event or censored)	Date of event or censoring
1	Patient had a documented acute ILD exacerbation or died within the first 52 weeks and the date of the event is known	Event	Earliest Date of event
2	Patient had a documented acute ILD exacerbation or died within the first 52 weeks and the date of the event is unknown	Event	Imputed date of event
3	Patient did not have a documented acute ILD exacerbation and is alive after 52 weeks	Censored	Day 373 (372 days after first drug intake)
4	Patient status is unknown	Censored	Date of last contact when the patient was known to be alive and event free

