5.3.1.1 Time to first non-elective hospitalisation or death over 52 weeks

Time to non-elective hospitalization assessment will be based on the date of hospitalization collected on a specific hospitalization eCRF page. The eCRF page will capture whether the non-elective hospitalization was due to respiratory cause, and the primary admission diagnosis according to the investigator. Cause of non-elective hospitalizations will not be adjudicated by the AC.

For those patients who either experience a non-elective hospitalisation or who die due to any cause within the first 52 weeks, time to first non-elective hospitalisation or death [days] will be computed as:

- Earliest of date of first non-elective hospitalisation or death – date of first drug intake + 1

Patients who did not experience any event within the first 52 weeks will be censored according to the mechanism for censoring as described in Table 5.3.1.1: 1.

Table 5.3.1.1: 1 Censoring Rules for Time to first non-elective hospitalisation or death over 52 weeks

Rule #	Situation	Outcome (event or censored)	Date of event or censoring
1	Patient had a documented non-elective hospitalisation or died within the first 52 weeks and the date of the event is known	Event	Earliest Date of event
2	Patient had a documented non-elective hospitalisation or died within the first 52 weeks and the date of the event is unknown	Event	Imputed date of event
3	Patient did not have a documented non-elective hospitalisation and is alive after 52 weeks	Censored	Day 373 (372 days after first drug intake)
4	Patient status is unknown	Censored	Date of last contact when the patient was known to be alive and event free

5.3.1.2 Absolute change from baseline in FVC at week 52

The absolute change from baseline in FVC at week 52 will be computed and shown. The evaluation will be done by assessing the absolute change in FVC in ml between week 52 and baseline; and in addition to that, by assessing the absolute change from baseline in FVC in % pred between week 52 and baseline. The changes in these two parameters between the two treatment groups will be depicted and described.

Specific rules of handling of missing items are detailed in [Section 6.6.2.1](#).

5.3.1.3 Absolute decline from baseline in FVC % pred at week 52

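### SAP 6.6.2.2 imputes partial exacerbation and hospitalisation dates without bounds, so events can fall before first dose or cross day 373, and it gives no date when the year is missing although the censoring tables need one

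*SAP*

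**What the plan says.** SAP 6.6.2.2 gives three rules for partial dates of acute ILD exacerbation and non-elective hospitalisation:

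- Day missing: "If day is missing, then imputed day will be the 15th of the month".
- Day and month missing: "If day and month are missing, then imputed date will be the 1st of July of the (non-missing) year".
- Year missing: "If year is missing, date will not be imputed".

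None carries a lower or upper limit. The next paragraph of the section treats a missing or incomplete date of death differently. It takes the earliest date that meets three limits. One is the start of the fatal event; the other two read: "and on or after treatment start (in case this AE is treatment emergent), and on or after date of last contact".

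Time is counted from first dose. For exacerbation, SAP 5.2.2.1.3 uses "Earliest of date of first documented acute ILD exacerbation or death – date of first drug intake + 1". For hospitalisation, SAP 5.3.1.1 uses "Earliest of date of first non-elective hospitalisation or death – date of first drug intake + 1". SAP 5.3.2.2 and 5.3.2.3 use the same formulas over the whole trial. SAP 6.1.1 limits the 52-week analyses to data from first drug intake to 372 days after it, that is, day 1 to day 373.

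Rule 2 of the censoring table in SAP 5.2.2.1.3 covers a patient who had a documented exacerbation or "died within the first 52 weeks and the date of the event is unknown". The patient counts as an event at the imputed date. Rule 2 in SAP 5.3.1.1 does the same for hospitalisation.

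**The concern.** A fixed calendar default takes no account of when the patient was on study. An event known to have happened after first dose can be placed before it, which gives a zero or negative time outside the SAP 6.1.1 period. An event inside the 52 weeks can be moved past day 373, and a Part B event can be moved back before it. With the year missing, Rule 2 calls for an imputed date that SAP 6.6.2.2 does not supply. A programmer could then code the patient as an event without a time or as censored, and the opening sentence of 6.6.2.2 lends support to censoring.

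Time to first acute exacerbation or death is a main secondary endpoint. SAP 7.5.2.1.3 also drops everything but frequencies if fewer than 5% of patients have an exacerbation over 52 weeks (5% of 600 is 30 patients), so a single misplaced date could matter if the count lay right at that threshold.

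**Working it through.** The documents give no event count, power or share of partial dates for these endpoints, so there is no design figure to reproduce. The one stated constant is consistent: 372 days after first intake is day 373 when 1 is added.

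**Step 1: apply the SAP's formula.** Time = imputed date − first drug intake + 1.

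| First dose | True event (day) | Recorded as | Imputed date | Time |
|---|---|---|---|---|
| 20 Mar 2017 | 28 Mar 2017 (9) | Mar 2017 | 15 Mar 2017 | −5 + 1 = −4 |
| 10 Sep | later the same year | year only | 1 Jul | −71 + 1 = −70 |
| 1 Oct 2017 | 20 Nov 2017 (51) | 2017 | 1 Jul 2017 | −92 + 1 = −91 |
| 1 Feb 2017 | 20 Jan 2018 (354) | 2018 | 1 Jul 2018 | 515 + 1 = 516 |
| 1 Sep 2017 | 20 Nov 2018 (446) | 2018 | 1 Jul 2018 | 303 + 1 = 304 |

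Rows 1 to 3 fall before first dose. Row 4 is a 52-week event moved out of the window. Row 5 is a Part B event moved into it.

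**Step 2: how often, given a partial date.** Every first-dose day of one calendar year was crossed with every true event day from 1 to 373. Uniform first-dose dates and uniform event days are assumptions.

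| Missing part | Time ≤ 0 | Time > 373 | Either |
|---|---|---|---|
| Day | 1.12% | 0.93% | 2.05% |
| Day and month | 12.37% | 12.10% | 24.47% |

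For events in the first 90 days, the shares with time ≤ 0 are 4.6% (day missing) and 38.0% (day and month missing); none exceeds 373.

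**Step 3: scale.** Assume 5% to 10% of 600 patients have an event (30 to 60) and 1% to 3% of the dates are partial.

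- Partial dates: 30 × 0.01 = 0.3 to 60 × 0.03 = 1.8.
- Placed at or before time 0: 0.3 × 0.0112 ≈ 0.003 to 1.8 × 0.1237 ≈ 0.22 events.
- Placed at or before time 0 or past day 373: 0.3 × 0.0205 ≈ 0.006 to 1.8 × 0.2447 ≈ 0.44 events.
- A deliberately extreme case, 60 events with 10% partial and all lacking day and month: 6 × 0.2447 ≈ 1.5 events.

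These counts leave out missing-year events and Part B events brought into the window; the documents give nothing from which to size either.

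**Step 4: missing year.** No arithmetic applies. Rule 2 needs an imputed date, 6.6.2.2 declines to produce one, and the two cannot both be carried out.

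**The case against.** The strongest reply is that this is an edge case with a stated intent. Rule 2 classes these patients as events. A reader might infer that a survival procedure would discard a non-positive time and the event would vanish. The documents do not say so: exclusion is software behaviour that no section describes. A patient with a later death or a later dated event inside the window would also still count. That part of the reply stands. The date itself is still wrong and outside the SAP's own analysis period.

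A reader might also infer that the error only removes true events. Row 5 of the worked examples shows that it can add them.

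A second reply is that SAP 6.6.3.2 sends incomplete AE dates to a company standard, and exacerbations come from the AE page. That standard may contain a bound. It is cited for safety endpoints, its content is not in the documents, and 6.6.2.2 is the endpoint-specific rule. Hospitalisation dates come from their own eCRF page, so an AE standard would not clearly cover them.

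A third reply is that a missing year is close to hypothetical. Inpatient hospitalisation is an SAE reportable within 24 hours (Protocol 5.3.6.1 and 5.3.7), a counted exacerbation needs CT findings, and both event types are recorded at scheduled visits. This is fair, and it makes the clash with Rule 2 a matter of wording more than of numbers.

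**Conclusion.** The point holds as a defect in a stated rule, with very small expected effect. SAP 6.6.2.2 can give an on-study event a non-positive time or carry it across day 373 in either direction, and its missing-year rule contradicts Rule 2 of the tables in SAP 5.2.2.1.3 and 5.3.1.1.

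The expected number of events misplaced out of the 52-week period is well under one, if 1% to 3% of 30 to 60 event dates are partial. Both ranges are assumed, as are uniform first-dose and event days. It would be tempting to treat every partial date (up to about 2) as a lost event and to express that as a share of the information. That overstates the loss: most partial dates stay within the window, and the composite also includes deaths.

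The reach is one main secondary endpoint with nominal, unadjusted p-values (Protocol 7.3.2, SAP 7.5), one exploratory endpoint with no p-values (SAP 7.6), and their whole-trial versions. The primary FVC analysis does not use these dates.

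**What to change.** Replace the partial-date rule in SAP 6.6.2.2 for any event known to have occurred after first dose, whether or not it is treatment-emergent:

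- Form the interval consistent with the recorded partial date. It starts no earlier than first drug intake and, where known, the last visit without the event. It ends no later than the earliest of the reporting visit, event end, death, last contact or data cut-off.
- Use the 15th or 1 July if it lies in that interval; otherwise use the interval midpoint.
- If the year is missing, use the midpoint between the last event-free visit and the reporting visit, so that Rule 2 can be applied.

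The limit should not depend on treatment emergence. Events more than 28 days after the last dose are not treatment-emergent (Protocol 7.3.4) but still count under the intent-to-treat principle (Protocol 7.3.2), so a floor at the start of AE reporting could still give them a negative time. The midpoint avoids piling events on day 1: with only the year known, the 10 September patient has the interval 10 September to 31 December and lands on 5 November, day 57. SAP Section 5 lets imputed dates feed the date of last contact, so the ceiling should use last contact without the date being imputed.

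The cost is a short SAP paragraph, minor extra programming and slightly approximate event times. With scheduled visits at most 16 weeks apart, a midpoint between two attended visits is off by no more than about 8 weeks, apart from visit windows.

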6.6.2.3 Categorical endpoints

In the analyses of the binary endpoints, patients with missing data will be considered as non-responders (worst case analysis).

6.6.3 Other variables

6.6.3.1 Concomitant therapies

In case of (partially) missing start and end dates of concomitant therapies, the dates will be imputed so that the extent of exposure to the concomitant therapy is maximal, i.e. the first day (month) of the month (year) for incomplete start dates and the last day (month) of the month (year) for incomplete end dates.

6.6.3.2 Safety endpoints

Missing or incomplete AE dates will be imputed according to BI standards ([7](#)).

6.6.3.3 Trial diagnosis date

In case of partially missing date of trial diagnosis, the following imputation will be done:

- If day is missing, then imputed day will be the 1st of the month
- If day and month are missing, then imputed date will be the 1st of January of the (non-missing) year
- If year is missing, date will not be imputed

6.6.3.4 Pharmacokinetic endpoints

Missing data and outliers of PK data are handled according to (4).

Handling of missing PK data will be performed according to the BI standard procedure (5).

6.7 BASELINE, TIME WINDOWS AND CALCULATED VISITS

As a general rule, the last assessment / measurement observed prior to start of trial medication will be assigned to baseline. Note that for some trial procedures (e.g. body weight, vital signs, laboratory tests) this may be the value measured on the same day trial medication was started. In these cases it will be assumed that the measurements were taken prior to the intake of any study medication (if the measurement time was not captured). If no further data available, this can also be the last screening assessment.

Visit windowing will be performed as described in [Table 6.7: 1](#), [Table 6.7: 2](#), [Table 6.7: 3](#) and [Table 6.7: 4](#), in order to assign data to the relevant study visit based on the actual day of the assessment. Data will be analysed using the re-calculated visits in the statistical tables. However, in the listings, all visits performed will be displayed (even if outside time-window), along with the re-calculated visit.

Table 6.7: 1 Time windowing rules for spirometry (FVC), physical exam, vital signs

Time window of actual day ^[1]			Allocated to		
Start (S _n) day	End (included) (E _n) day	Length of the time-window [days]	Visit number (n)	Visit name	Planned day of the visit (V _n)
-84	1	85	2	Baseline	1
2	22	21	3	2 weeks	15
23	36	14	4	4 weeks	29
37	64	28	5	6 weeks	43
65	127	63	6	12 weeks	85
128	211	84	7	24 weeks	169
212	309	98	8	36 weeks	253
310	373	64	9	52 weeks	365
374 (S _p)	E _p = (V _p + V _{p+1})/2 = 533	E _p -S _p +1 = 160	10	68 weeks	477 (V _p)
E _p + 1	(V _{p+1} + V _{p+2})/2	E _{p+1} -S _{p+1} +1	11	84 weeks	589 (V _{p+1})
...	Every weeks thereafter	16
					...

^[1] First trial drug intake date is taken into account as a reference to calculate time windows

Table 6.7: 2 Time windowing rules for K-BILD, L-PF, PF-IQOLs, SpO₂

Time window of actual day ^[1]			Allocated to		
Start day	End day (included)	Length of the time-window [days]	Visit number	Visit name	Planned day of the visit
-84	1	85	2	Baseline	1
2	127	126	6	12 weeks	85
128	211	84	7	24 weeks	169
212	309	98	8	36 weeks	253
310	373	64	9	52 weeks	365

^[1] First trial drug intake date is taken into account as a reference to calculate time windows

Note: SpO₂ not measured at visits 6 and 8

Table 6.7: 3 Time windowing rules for DLCO

Time window of actual day ^[1]			Allocated to		
Start (S _n) day	End (included) (E _n) day	Length of the time-window [days]	Visit number (n)	Visit name	Planned day of the visit (V _n)
-84	1	85	2	Baseline	1
128	211	84	7	24 weeks	169
310	373	64	9	52 weeks	365
374 (S _p)	$E_p = (V_p + V_{p+1})/2 = 533$	$E_p - S_p + 1 = 160$	10	68 weeks	477 (V _p)
E _p + 1	$(V_{p+1} + V_{p+2})/2$	$E_{p+1} - S_{p+1} + 1$	11	84 weeks	589 (V _{p+1})
...	Every 16 weeks thereafter	...

[1] First trial drug intake date is taken into account as a reference to calculate time windows

Table 6.7: 4 Time windowing rules for laboratory measurements (and pregnancy test)

Time window of actual day ^[1]			Allocated to		
Start day	End day (included)	Length of the time-window [days]	Visit number	Visit name	Planned day of the visit
-42	1	43	2	Baseline	1
2	22	21	3	2 weeks	15
23	36	14	4	4 weeks	29
37	64	28	5	6 weeks	43
65	106	42	6	12 weeks	85
107	148	42	6a	18 weeks	127
149	190	42	7	24 weeks	169
191	232	42	7a	30 weeks	211
233	281	49	8	36 weeks	253
282	337	56	8a	44 weeks	309
338	373	36	9	52 weeks	365
374	449	76	9a	60 weeks	421
450	505	56	10	68 weeks	477
506 (S _p)	$E_p = (V_p + V_{p+1})/2 = 561$	$E_p - S_p + 1 = 56$	10a	76 weeks	533 (V _p)
E _p + 1	$(V_{p+1} + V_{p+2})/2$	$E_{p+1} - S_{p+1} + 1$	11	84 weeks	589 (V _{p+1})
...	Every 8 weeks thereafter	...

[1] First trial drug intake date is taken into account as a reference to calculate time windows

If after windowing of visits at baseline, two or more values fall within the same baseline interval, then the last value prior to first drug intake will be taken into account. If after windowing of post-baseline visits, two visits fall in the same interval, then the measurement

closest to the planned visit will be taken into account. In case two measurements are equidistant from the planned visit, then the last one will be picked.

7. PLANNED ANALYSIS

Planned analyses can be categorized based on:

- The study period for which they are performed:
 - Over 52 weeks (Part A) and over the whole trial (Part A and Part B together)
- The study population for which they are performed:
 - The co-primary populations (“overall” population or sub-population of patients with “HRCT with UIP-like fibrotic pattern only”), or the complementary patient population of patients with “other HRCT fibrotic patterns”.

Unless specified otherwise, analyses over 52 weeks (Part A) and over the whole trial (Part A and Part B) will be produced on both co-primary populations. In addition, selected analyses over 52 weeks and over the whole trial will be produced on the complementary population of patients with “other HRCT fibrotic patterns”. Details can be found in subsequent sections. Please note that analyses based on the complementary population will, by default with only few exceptions, be part of the CTR appendix.

The labelling and display format of statistical parameters will follow BI standards (9). For End-Of-Text tables, the set of summary statistics is: N / Mean / SD / Min / Median / Max. In descriptive statistics tables, mean, sd and median will be rounded to one additional digit than the raw individual value. In case extreme data outside of the expected range are observed, quartiles and percentiles will be presented additionally.

Tabulations of frequencies for categorical data will include all categories depicted in the eCRF and will display the number of observations in a category as well as the percentage (%) relative to the respective treatment group (unless otherwise specified, all patients in the respective patient set whether they have non-missing values or not). Percentages will be rounded to one decimal place. The category missing will be displayed only if there are actually missing values.

If not otherwise specified, two-sided p-values and confidence intervals will be displayed. Please note that the depiction of p-values in outputs will be limited to the following evaluations:

- Primary analysis performed in both co-primary populations
- Sensitivity analyses of the primary endpoint analysis in both co-primary populations
- Nominal p-values for the evaluation of the main secondary endpoints, evaluated in both co-primary populations
- Interaction p-values for the efficacy evaluations in the subgroup analyses

The primary analyses will include all treated patients.

7.1 DEMOGRAPHIC AND OTHER BASELINE CHARACTERISTICS

A table in the CTR will present the number of patients screened, randomised and treated. The number of patients prematurely discontinuing their study treatment will be shown with the reasons for discontinuation. The number and percent of patients completing the end of treatment visit and the number of patients with treatment ongoing will also be presented. Please note there will be ongoing patients at the time of the data cut-off for the primary analysis; at the time point when the final analysis will take place there will not be any more ongoing patients in this trial. Where percentages are shown, the denominator will be the number of patients treated in each treatment group.

Descriptive statistics as well as frequency counts will be provided for all demographic and baseline characteristics depicted in [Section 5.4.1](#). The CTR tables will show the relevant descriptive statistics (number and percent within categories; other descriptive statistics for continuous variables) by treatment arm.

7.2 CONCOMITANT DISEASES AND MEDICATION

Only descriptive statistics are planned for this section of the report.

7.2.1 Baseline conditions and cardiovascular medical history

The baseline conditions will be included as coded items using the current Medical Dictionary for Regulatory Activities (MedDRA) version in use at BI at the time of database lock. They will be summarised by MedDRA system organ class (SOC) and Preferred Term. The CTR table will show the counts of patients with a Baseline condition in each SOC present (SOC sorted by standard European Medicines Agency (EMA) order) and then the conditions (preferred terms) under that SOC in descending order of overall prevalence. This summary will be produced on all patients and by the patient's underlying HRCT patterns.

The relevant cardiovascular medical history will be summarised, with particular focus on myocardial infarction, transient ischemic attacks, stroke, cardiac arrhythmia and heart failure.

